#### I. Background and Purpose

Chronic inflammatory demyelinating polyneuropathy (CIDP) is a chronic immune-mediated disease of the peripheral sensory motor nerves characterized by motor weakness, sensory loss, muscle wasting and loss of motor ability. Majority of CIDP cases are idiopathic with insidious onset, relapsing remitting course and prolonged (over years) clinical course. CIDP incidence is unknown in pediatric population however it is a rare treatable cause of neuromuscular weakness in children. Treatment of CIDP involves chronic use of steroids, intravenous immunoglobulin (IVIG) and rarely plasma exchange (PLEX). Outcome measures such as patient reported motor disability scores, electrophysiology parameters, functional motor strength testing are available to look for interval change. Despite above mentioned treatments majority of patients have tremendous disease burden. There is a need for alternative/adjunctive therapies that can decrease chronic inflammation effectively and safely in pediatric CIDP patients.

Vagus nerve stimulation has received significant scientific and clinical attention and has been shown to effectively reduce systemic inflammation. Results from early clinical trials for treatment of Rheumatoid Arthritis (NCT01552538, NCT01552941, ClinicalTrials.gov) have demonstrated significant lifestyle benefits and reduced symptoms in RA patients. Similar benefits of VNS have been observed in Crohn's patients (NCT02311660). In these studies, patients are surgically implanted with a stimulator and electrodes directly on the nerve. Preliminary results have demonstrated safety and efficacy in patients that previously were unresponsive to traditional pharmacological therapies. Unfortunately, surgical implantation of a device is difficult and costly.

Recent investigations have significantly increased our understanding of nVNS. Compared to traditional implanted vagus nerve stimulation devices, nVNS uses electrodes placed on the skin surface to stimulate the vagus nerve. Non-invasive vagus nerve stimulation (nVNS) has shown promise in animal and human models to reduce chronic inflammation in multiple disease states. By delivering electrical pulses at the skin surface above the vagus nerve, neural pathways involved in regulating systemic inflammation are activated. Using a handheld device, patients apply brief durations of stimulation multiple times per day to achieve therapeutic benefit. nVNS is currently FDA approved for clinical use in the treatment of migraines and cluster headaches, with on-going clinical studies on epilepsy and systemic inflammation. Preliminary published results have demonstrated significant therapeutic benefit to the patients with minimal side-effects such as a feeling of paresthesia at the site of the electrodes which subsides after turning the

stimulation off.

#### **Hypotheses**

# We hypothesize that nVNS therapy can reduce systemic inflammation in CIPD patients, functionally halting degradation of motor nerve conduction and hand grip strength.

The specific aims of this proposal are to:

- 1. Quantify functional changes in motor nerve conduction studies, hand held grip strength, and Rash-built Overall Disability Scale (R-ODS) in CIDP patients receiving standard of care treatment and daily nVNS.
- 2. Characterize changes in serum cytokine profiles in patients receiving standard of care treatment and daily nVNS.

We anticipate observing a reduction in serum TNF- $\alpha$  levels after nVNS therapy, consistent with previously published clinical results. Serum cytokine levels will be statistically analyzed on a per patient basis, with each patient's baseline measurements used for comparison. will be used to determine statistically significant differences between subsequent serum cytokine profiles for the entire patient population and NCS metrics. Pearson's correlation coefficient will be used to understand the relationship between changes in serum cytokine levels and NCS metrics. Pearson's correlation coefficient will also be used to assess the relationship between number of therapy session (as reported by the patient) and serum cytokine levels.

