#### II. Summary of Procedures

All proposed studies will be conducted at Children's Healthcare of Atlanta (Atlanta, GA) for a total duration of 24 months. Local institution review board approval would be obtained prior to the study. The table below (Table 1) provides an overview of the timeline and specific tasks to be completed upon each visit. Baseline represents the initial visit after the patient has been screened and meets the inclusion criteria (EKG results may take 24-48 hrs and study participant will be advised to start the study intervention once confirmation of normal EKG is obtained) Patients will be scheduled to visit the clinic for follow up visits at the pre-set time points shown. A total of 15 subjects, from age 5 years to 21 years, will be included in the study. The stimulation devices used in this study are VitalStim 400, electrical neuromuscular stimulators, which have been used in multiple previous clinical studies for modulation of pain and have received FDA approval. The (2) electrodes for the device will be placed on the subjects left cervical (neck) region. The stimulator will be placed in a comfortable position, such as next to the pillow. The stimulators are battery-powered and allow configuration of the stimulation parameters to the comfort of the patient. Parents will be trained on where to place electrodes, how to ensure that the electrodes make a good contact with the skin, and how to set the stimulation parameters.

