#### SCHEDULE of Events

STUDY PROCEDURES (*experimental procedure)	Baseline	3 mon	6 mon	9 mon	12 mon	15 mon	18 mon	21 mon	24 mon
Informed consent	x								
Inclusion/exclusion criteria	Х								
Medical history	Х	х	х	х	х	х	х	х	х
*nVNS 2 times daily x 60 mins each (log book maintained and reviewed)	x	x	x	x	x	x	x	x	x
Physical and neurological examination	x		х		х		х		х
Vital Signs	Х		х		х		х		х
Cytokine profile	Х		х		х		х		х
EKG	Х		х		х		х		х
R-ODS scale and handheld dynamometer	х		х		х		х		х
Nerve conduction study	x				х				х
Adverse events	х	х	х	х	х	х	х	х	х
Concomitant medications (IVIG, steroids, PLEX)	х	х	х	х	х	х	х	х	х
Telephone visit/ check (To limit inperson visits due to COVID-19 pandemic)		х		х		х		x	

**Table 1. Study outline for nVNS in CIDP patients.** Patients will be followed for two years with nVNS as an adjunctive to standard IVIG therapy. Patients will be validated against the stated inclusion criteria prior to enrollment in the study. Baseline measurements before nVNS is added will be taken to determine change in physiological and functional outcomes over time. All procedures other than in-home vagus nerve stimulator therapy will take place at CHOA under the direct guidance of the PI. Parents will be trained on where to place electrodes, how to ensure that the electrodes make a good contact with the skin, and how to set the stimulation parameters. Patient is not required to have anyone sit with them during the stimulation procedure. At the end of two years, we will understand the benefits (or not) of nVNS in CIDP and the compliance of nVNS therapies in pediatric patients.

Specific Aim 1: Quantify functional changes in motor nerve conduction studies, hand held grip strength, and Rasch-built Overall Disability Scale (R-ODS) in CIDP patients receiving standard of care treatment and daily nVNS.

• **nVNS Therapy.** The nVNS therapy will be delivered using a handheld electrical neuromuscular stimulator

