# Specific Aim 2: Characterize serum cytokine profiles in CIDP patients receiving standard of care treatment and daily nVNS.

Stimulation of the vagus nerve has been shown to reduce pro-inflammatory cytokine levels in both animal and human investigations just after one session. In addition to evaluating functional changes in CIDP patients, we will quantify pro-inflammatory cytokine levels known to be elevated in CIDP patients. Serum cytokine assay available at Children's Healthcare of Atlanta laboratory will be used (https://www.testmenu.com/choa/Tests/671572). The assay contains 13 cytokines (interleukin 2, 4, 5, 6, 8, 10, 12, 13, 17, interleukin 1 beta, tumor necrosis factor alpha, interferon gamma, interleukin 2 receptor (SD25) soluble). Available normative laboratory values for above-mentioned cytokines will be compared with the CIDP subject values. Blood samples will be collected at baseline and each subsequent follow up visit as shown in Table 1 for profiling of serum cytokine levels. By correlating physiological (changes in cytokine levels) and functional effects (NCS, R-ODS, grip strength), we will develop a mechanistic basis for how and why nVNS benefits pediatric CIDP patients.

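### The session-count correlation is written on cytokine levels rather than baseline-adjusted levels, which may cost power that the collected baseline could recover

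*Combined protocol and SAP*

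**What the plan says.** Three statements in section I, under Hypotheses, bear on how cytokines are analysed.

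- A general rule: "Serum cytokine levels will be statistically analyzed on a per patient basis, with each patient's baseline measurements used for comparison".
- A first correlation: "Pearson's correlation coefficient will be used to understand the relationship between changes in serum cytokine levels and NCS metrics".
- A second correlation, of exposure with response, for which Pearson's coefficient is "used to assess the relationship between number of therapy session (as reported by the patient) and serum cytokine levels".

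The first correlation is on changes and the second is on levels. No baseline covariate is written for the second. The plan also does not say which visits enter it, whether sessions are counted cumulatively or per interval, or how several samples from one child are combined.

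The note to Table 1 gives the purpose of the baseline data: "Baseline measurements before nVNS is added will be taken to determine change in physiological and functional outcomes over time". Table 1 schedules cytokines at baseline, 6, 12, 18 and 24 months, and nerve conduction studies (NCS) at baseline, 12 and 24 months only. On size, section II says: "A total of 15 subjects, from age 5 years to 21 years, will be included in the study". No significance level, power, SD or within-child correlation is stated.

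**The concern.** Children aged 5 to 21 on differing background treatment may well start at different cytokine levels. If those differences persist to follow-up, they are noise in a correlation of sessions with follow-up level. The baseline sample would remove part of that noise, and the sentence as written does not use it.

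This is the only exposure-response analysis that the plan specifies. With 15 children there is little power to spare, and a real relationship that was missed could be read as evidence that more stimulation does not lower cytokines.

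The silence on visits matters too. Four post-baseline samples from each of 15 children make 60 values. An analyst could put all 60 into one Pearson test, which would treat repeated samples from a child as independent.

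**Working it through.** The plan states no power figure, so there is none to reproduce.

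**Inputs from the documents:** n = 15; one baseline and four post-baseline cytokine samples per child.

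**Assumptions:** two-sided 5% test, no dropout, one post-baseline value per child, normal data, session count independent of baseline. ρ is the correlation between a child's baseline and follow-up values. b is the slope in cytokine SDs per SD of sessions. Neither is in the documents, so both are varied.

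**Step 1: what 15 children can detect.** The critical t on 13 df is 2.160, so the critical |r| is 2.160/√(2.160² + 13) = 0.514. By Fisher's z, 80% power needs a true r of tanh((1.960 + 0.842)/√12) = 0.67. Power is 19% at r = 0.3 and 48% at r = 0.5.

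**Step 2: noise under each analysis.** Let follow-up = ρ × baseline + b × sessions + error, with error variance 1 − ρ². Apart from the session effect, the variance left is:

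- level: 1, whatever ρ is;
- change from baseline: 2(1 − ρ);
- level with baseline as covariate: 1 − ρ².

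Change is noisier than level when 2(1 − ρ) > 1, that is, when ρ < 0.5. The covariate analysis never leaves more variance than level, but it spends one degree of freedom.

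For b = 0.5, the true correlation of sessions with level is 0.5/√(0.25 + 1) = 0.447 at every ρ. With baseline adjustment at ρ = 0.8 it becomes 0.5/√(0.25 + 0.36) = 0.640.

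**Step 3: power by simulation**, b = 0.5 (20,000 runs per cell; repeat runs agree to about a percentage point):

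| ρ | Variance, change | Variance, adjusted | Power, level | Power, change | Power, adjusted |
|---|---|---|---|---|---|
| 0 | 2.00 | 1.00 | 40% | 23% | 37–38% |
| 0.3 | 1.40 | 0.91 | 40% | 31% | 41% |
| 0.5 | 1.00 | 0.75 | 40% | 40% | 47% |
| 0.7 | 0.60 | 0.51 | 40% | 58% | 61% |
| 0.8 | 0.40 | 0.36 | 40% | 75% | 74% |
| 0.9 | 0.20 | 0.19 | 40% | 94% | 92% |

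With b = 0.3, level has about 18% power and the adjusted analysis 17%, 18%, 21%, 28%, 38% and 59% down the same rows. With b = 0.7, level has about 65% and adjusted 61%, 65%, 72%, 85%, 93% and 99%.

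**Step 4: pooling visits.** With no true relationship, one Pearson test on all 60 values rejects in 10% to 27% of simulated trials instead of 5%. This assumes intraclass correlations of 0.3 to 0.8 for the cytokine and 0.5 to 0.8 for sessions. Step 3 uses one value per child, so it does not measure what a four-visit model would add.

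**The case against.** The strongest reply is that the general rule already covers this correlation: each child's baseline is the comparator for cytokines, and Table 1 says why baseline is taken. On that reading, the missing word is a drafting slip. The text just before the two correlations is also incomplete in the public copy, so a method may be named there that cannot be seen. This stands in part. A reader might infer that the plan disregards baseline altogether, and the documents do not support that. They leave it unclear whether the rule extends to the session correlation, and the neighbouring sentence does say changes where changes are meant.

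A second objection is that the size of the loss is assumed. This also stands. A reader might infer that between-child differences would swamp any dose-response, or that most of the power is wasted. Such figures can be produced. With a true correlation of 0.7 between sessions and the log ratio to baseline (SD 0.5), and a log-baseline SD of 1.0, Pearson on level has about 15% power against 87% for the log ratio. But that setting implies a baseline to follow-up correlation of 1/√1.25 = 0.89 on the log scale, and it places the true effect on the scale that wins. At a log-baseline SD of 0.25, level has 70%. If the effect is additive on the raw scale (log-baseline SD 0.6), raw change has 88% and the log ratio 70%.

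A reader might also extend the criticism to the NCS correlation. That analysis already uses change, and faulting its raw scale would need data on skewness and spread that the documents do not contain.

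**Conclusion.** The point holds as a conditional loss of power and a gap in specification. As written, the session correlation uses levels, departs from the adjacent sentence, and leaves the handling of baseline and of repeated samples open.

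At n = 15 and a slope of 0.5 SD, the loss against baseline adjustment is about 7 points at ρ = 0.5, 21 at 0.7, 34 at 0.8 and 52 at 0.9, and nothing at 0.3 or below. Level falls below half the power of the adjusted analysis only near ρ = 0.8 (slope 0.3) to 0.9 (slope 0.5).

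With one visit per child and no true relationship, false positives stay near 5%, so the harm is missed relationships. False positives rise only if visits are pooled as independent, which the plan neither states nor rules out.

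Adjustment does not cure the small sample. At a slope of 0.3 SD and ρ = 0.7, adjusted power is still only 28%.

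**What to change.** In section I, under Hypotheses, replace the session-count Pearson analysis with a mixed model for each cytokine:

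- outcome: the cytokine value at 6, 12, 18 and 24 months;
- exposure: sessions reported in the interval before that blood draw;
- covariate: the child's own baseline value of that cytokine, with both on the log scale if the values are skewed;
- child as a random effect, so that repeated samples are not treated as independent.

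Use baseline as a covariate rather than a plain change score or log ratio, because change scores lose power when the within-child correlation is below 0.5. Give Spearman's rho as a sensitivity analysis at one named visit, so that each child contributes one pair.

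Leave the NCS correlation on change and state that it uses the 12 and 24-month visits. The four-visit model does not fit it, because NCS is not measured at 6 or 18 months.

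Cost: a few lines of plan text and code, and no new data. If baseline turns out uninformative, the price is 2 to 3 points of power at a slope of 0.5 SD (40% against 37–38%), about 1 point at 0.3 and about 4 at 0.7.

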CHOA PI: [name] Study Protocol Version: 09/16/2021 (VitalStim 400) device. It is safe, effective at stimulating the vagus nerve, and easy to use by patients outside the clinic. Electrical neuromuscular stimulator devices have been used for years in pain-related preclinical and clinical research. Patients will be requested to deliver nVNS 2 times per day for 60 minutes each time for at least 5 days per week. The stimulation frequency (number of pulses) and amplitude (amount of current) will be set during the initial baseline session in the clinic and will be set to prevent discomfort to the patient or impact cardiorespiratory parameters. Initial stimulation parameters will be guided by previous reports of nVNS in patients. Patients will be trained on all appropriate methods for using the devices and asked to report the number of daily therapy sessions completed. Patients will be asked to continue their standard medication regimens which include in majority of cases 3 weekly IVIG (1 gm/kg) infusions, with or without steroids and plasma exchange.

- Handheld dynamometer: In the pediatric NM clinic we use a Jamar Handheld Dynamometer with reference range (in kilograms and pounds) for children ages 5-18 years. Both right and left hand grip strength would be measured. Best of the three attempts will be used in each hand. We routinely use dynamometer.
- **R-ODS:** Twenty four item motor scale based on day to day activities with a score of 0-48. The scale was designed for adult CIDP subjects however based on our experience in children the scale captures pediatric motor disability as well.
- NCS metrics: Motor nerve conduction studies are well tolerated in children. We routinely study median, ulnar, common fibular and tibial nerves on one side of the body. Distal and F wave latency, conduction velocity and amplitude will be recorded in all nerves. In addition, drop in motor amplitude and or temporal dispersion on proximal stimulation will be noted.

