#### III. Risks

Pediatric CIDP is a rare condition and disease course if often prolonged with relapse and remissions. The subject sample size is small and meaningful clinical/biochemical changes following an intervention in CIDP patient population takes months to years. In general, these limitations are true for the majority of rare pediatric neuromuscular conditions. Alternative approaches include comparing the study population with historical controls however well-done natural history studies in pediatric CIDP are missing. We also anticipate patient compliance challenges. The usage monitor on the nVNS device will allow us to account for that in the data analysis.

nVNS at the level of the neck in children has been used in multiple studies. Patients may experience irritation at the site of stimulation; however this typically subsides within 10-15 minutes post-stimulation. In addition, patients may experience soreness in the neck due to activation of muscles, which is expected to be temporary.

Rarely, EKG changes have been described with nVNS. The study design includes regular EKG checks and if any changes or abnormalities are noted, this will be deemed as serious adverse event (SAE) and lead to termination of device use in the study participants. A follow-up visit and EKG will be performed for these subjects and if EKG abnormalities persist, pediatric Cardiology evaluation will be requested.

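### The plan relies on the device's usage monitor to account for compliance, but schedules no reading of it, and its one exposure analysis uses patient-reported sessions

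*Combined protocol and SAP*

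**What the plan says.** All references are to the combined protocol and SAP.

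- **III. Risks.** The plan states "We also anticipate patient compliance challenges" and gives one remedy: "The usage monitor on the nVNS device will allow us to account for that in the data analysis". The monitor is mentioned nowhere else.
- **Schedule of Events, Table 1.** The treatment row reads "nVNS 2 times daily x 60 mins each (log book maintained and reviewed". No row covers reading or downloading the monitor. Cytokines are drawn at baseline and at 6, 12, 18 and 24 months. The contacts at 3, 9, 15 and 21 months are in the row "Telephone visit/ check (To limit inperson visits due to COVID-19 pandemic".
- **Table 1 caption.** "Patient is not required to have anyone sit with them during the stimulation procedure". After two years the study is to have learned about "the compliance of nVNS therapies in pediatric patients". No source, measure or threshold is given.
- **Specific Aim 1, nVNS Therapy.** Patients are "asked to report the number of daily therapy sessions completed".
- **Hypotheses, analysis paragraph.** The one exposure analysis is a Pearson correlation between "number of therapy session (as reported by the patient) and serum cytokine levels". The paragraph also says that cytokine levels are analysed patient by patient against each patient's own baseline. One of its sentences has lost its subject. That sentence concerns cytokine profiles and nerve conduction, and nothing here rests on it. The exposure sentence is complete.

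**The concern.** The plan names an objective record as its safeguard against poor compliance, then describes collecting and analysing only what the patient reports. Someone following the text would run the exposure correlation on self-report and would find no instruction to read the monitor.

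Two results are exposed. The first is the compliance conclusion, which the plan treats as something the study will deliver. Sessions logged but not done raise that figure directly. The second is the exposure-cytokine correlation. The trial has one arm, so this relation is one of its few internal checks, although a weak one.

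The effect on the correlation depends on the type of error:

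- Random error that varies between patients attenuates it.
- Uniform linear over-reporting leaves Pearson's r unchanged.
- Error related to outcome could bias it in either direction.

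**Working it through.** The documents give no power calculation, effect size or expected compliance, so there is no planned figure to reproduce. From the documents: n = 15, four post-baseline draws, and two 60-minute sessions a day on at least 5 days a week. Assumed: two-sided 5% level, one value per child, one cytokine, and all true correlations, reliabilities and over-reporting shares.

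**1. Compliance.** If a share s of missed sessions is logged as done, reported = true + s × (1 − true).

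| True | s = 10% | s = 25% | s = 50% |
|---|---|---|---|
| 70% | 73% | 77.5% | 85% |
| 50% | 55% | 62.5% | 75% |

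For example, 0.50 + 0.25 × 0.50 = 0.625.

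**2. Correlation with random reporting error.** With reliability ρ, the expected correlation is r√ρ. Fisher-z power is Φ(√(n−3) × atanh(r√ρ) − 1.96), plus a negligible lower tail. At n = 15 the critical |r| is 2.160/√(13 + 2.160²) = 0.514. Worked case, r = 0.5 and ρ = 0.7: r√ρ = 0.418, atanh = 0.446, × √12 = 1.544, and Φ(−0.416) = 34%.

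| True r | ρ = 1.0 | 0.8 | 0.7 | 0.5 |
|---|---|---|---|---|
| 0.3 | 19% | 16% | 14% | 12% |
| 0.4 | 31% | 25% | 23% | 17% |
| 0.5 | 48% | 38% | 34% | 25% |
| 0.65 | 77% | 63% | 56% | 41% |

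Simulation with the exact t test (40,000 trials) agrees within about 3 points, for example 50% at r = 0.5 and ρ = 1.0. An observed r of 0.5 has a 95% CI of tanh(0.549 ± 1.96/√12), that is −0.02 to 0.81.

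**3. Over-reporting by low users only.** Take true weekly use as Normal(8, 3) limited to 0–14, with users below 10 a week closing 50% or 80% of their gap to 10. A true r of −0.50 becomes −0.49 or −0.45. Mean compliance against 10 a week rises from 75.5% to about 88% or 95%. The correlation hardly moves, so it would not reveal the distortion.

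**4. Baseline adjustment, one averaged value per child.** Exposure is assumed unrelated to baseline. If baseline and follow-up correlate at b, the partial correlation is r/√(1 − b²); for r = 0.5 and b = 0.7 that is 0.5/√0.51 = 0.70. Simulated power:

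| True r | Level only | Adjusted, b = 0 | 0.3 | 0.5 | 0.7 |
|---|---|---|---|---|---|
| 0.5 | 50% | 47% | 51% | 62% | 85% |
| 0.3 | 19% | 18% | 20% | 23% | 34% |

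With no true relation, type I error stays at 4.8% to 5.2% for the level analysis and 4.9% to 5.1% with adjustment.

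**5. Compliance denominator.** Over 26 weeks, 2 × 5 × 26 = 260 sessions, or 2 × 7 × 26 = 364 if Table 1 is read as every day. A patient with 260 sessions is then 100% or 260/364 = 71% compliant.

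**The case against.** The strongest reply is that two sources can coexist: self-report for the cytokine correlation and the monitor for compliance. The Risks section is the only place that links a data source to compliance, and that source is the monitor. A missing table row does not prove that no reading will be taken. This stands as far as it goes: the documents leave the monitor's use undescribed and do not exclude it. It does not supply a reading time, a derived variable or an analysis.

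Four stronger readings are tempting, and the documents do not support them.

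- *The monitor has no role.* The Risks section gives it a general one; the operational role is missing.
- *The compliance conclusion is stated to rest on self-report.* The Table 1 caption names no source. Self-report is an inference from the records the plan describes.
- *The exposure analysis ignores baseline or pools visits.* The Hypotheses section compares each patient with baseline and works per patient. It uses changes in cytokines for the nerve conduction correlation and plain levels for the exposure correlation, and gives no rule for several draws per child. These are ambiguities.
- *Table 1 and Specific Aim 1 contradict each other on session numbers.* One can be read as sessions per treatment day and the other as a minimum number of days, so both can hold.

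It is also fair to say that the consequence rests on assumed figures, that no decision is tied to compliance, and that the power figures are for one cytokine when the assay has 13.

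**Conclusion.** The point holds as a gap between a stated safeguard and the described data collection and analysis. The monitor is relied on to account for compliance, yet no reading is scheduled and no analysis is assigned to it, while the only exposure analysis specifies patient-reported sessions.

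The main consequence is for the compliance conclusion, and only if it is drawn from the log book or patient report. On the assumed shares, the inflation runs from 3 points (70% reported as 73%) to 25 points (50% reported as 75%).

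For the correlation, the loss is small when the true relation is weak (19% to 14% power at r = 0.3 and reliability 0.7) and larger when it is strong and reports are poor (77% to 41% at r = 0.65 and reliability 0.5). Better exposure data would not make 15 patients enough for a firm conclusion. The change is worth making because it is cheap and makes the plan consistent. Confidence is medium, because the documents do not say what the monitor records or whether it can be downloaded.

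**What to change.** First confirm that the monitor's record can be retrieved and what it counts (sessions, minutes or both).

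**If it can be read:**

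- Add a reading to Table 1 at the 6, 12, 18 and 24 month in-person visits, which are also the post-baseline blood-draw visits.
- In the Hypotheses section, replace the patient-reported count with monitor-recorded use per week in the interval before each draw.
- Use the same record for the compliance conclusion. Keep the log book as backup where a reading is missing, and report agreement between the two.

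**If it cannot:** correct the sentence in III. Risks and state that exposure and compliance are self-reported.

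**In either case:**

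- Label the exposure analysis exploratory and adjust for the baseline cytokine value already collected.
- Use one value per child (mean weekly use and mean post-baseline cytokine), or a model that allows for repeated visits. Do not treat visits from one child as independent.
- State the compliance denominator and how the session statements in Table 1 and Specific Aim 1 fit together. No session rule is proposed here.

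**Cost:** a short reading at four visits already scheduled and a few sentences of text, or one corrected sentence and a statement on self-report if the monitor cannot be read. The monitor's accuracy must be checked first. Baseline adjustment costs about 1 to 3 points of power if baseline is unrelated to follow-up. Confounding by self-selected use remains whichever record is used.
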